6.2 SAFETY ENDPOINTS

The analysis of safety will be realized thanks to following endpoints:

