A number of publications support the hypothesis that dose titration of axitinib in a select group of patients who tolerate the drug at the standard starting dose may improve the efficacy [18-20].

Indeed, there is a variable level of drug exposure between patients and a significant percentage of patients are below the therapeutic drug threshold. Pharmacokinetic data suggest that normalization of plasma exposures can be achieved with dose titration [20, 21].

Clinical parameters for dose titration based on individual tolerability are useful for identifying patients with sub-therapeutic axitinib exposure at the 5 mg BID starting dose. Recent studies support an association between hypertension, Axitinib dose/plasma concentration and clinical outcome [22]. A retrospective analysis across 5 phase II studies of axitinib for the treatment of different solid tumor types shows that axitinib efficacy correlated with diastolic blood pressure \geq 90 mm Hg [23]. Recent results of a pharmacokinetic analysis also support axitinib dose titration to increase plasma exposure in patients who tolerate axitinib and demonstrate diastolic blood pressure as a potential marker of efficacy [20].

Axitinib, Inlyta[®]
A4061078 NON-INTERVENTIONAL STUDY PROTOCOL
ADONIS Amended V13
28 Sept 2017

In a randomized phase II clinical trial with axitinib for first-line metastatic RCC, the best response rate was obtained in patients with the highest rate of hypertension (82%) at baseline and thus who were not titrated. It suggests that these patients had adequate plasma exposure at the starting dose and that diastolic blood pressure could be considered as a marker of efficacy [24].

Dose increase or dose reduction of axitinib (Inlyta®) is labeled in the SmPC. The flexible dosing gives the physicians the option and flexibility to tailor the dose to each individual patient in order to optimize outcomes. Blood pressure appears as a potential predictive biomarker to define the suitable dose schedule. Though, the association between hypertension, Axitinib titration and clinical outcome needs to be further investigated.

ADONIS will allow assessing flexible dosing usage across Europe in real life and evaluate the impact of dose titration on the treatment outcomes of Axitinib in 2nd line mRCC patients post Sunitinib.

Gap 3:

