8.3. Variables

Variable	Role	Data source(s)
Patient demographics (year of birth, gender, height, weight)	baseline characteristics	Initiation visit
Performance status (ECOG, Karnofsky)	baseline characteristics, potential confounder	Initiation visit Follow up visit
Risk groups (MSKCC risk, Heng risk)	baseline characteristics, potential confounder	Initiation visit
Comorbidities	baseline characteristics, potential confounder	Initiation visit
Lab tests (abnormal findings – levels when abnormal)	baseline characteristics, potential confounder	Initiation visit Follow up visit
Blood Pressure measurement (Y/N, date of exam and level, antihypertensive treatment)	baseline characteristics, outcome	Initiation visit Follow up visit
Electrocardiogram (Y/N/date of exam/ abnormal findings)	baseline characteristics,	Initiation visit
Echocardiography (Y/N/date of exam/ abnormal findings, LVEF)	baseline characteristics,	Initiation visit
Tumor history (date of first diagnosis, TNM, Grade at diagnosis /at enrolment, Histology)	baseline characteristics	Initiation visit
Metastasis (date of first detection and	baseline characteristics	Initiation visit

localisation)		
Previous treatments for RCC (Surgery, radiotherapy, other / for primary tumor/ for metastasis)	baseline characteristics, potential confounder	Initiation visit
Sunitinib therapy (starting date and dose, dose change, change of schedule)	exposure	Initiation visit Follow up visit
Axitinib therapy (starting date and dose, dose titration up, dose reduction, change of schedule)	exposure, effect modifier/sub-group identifier	Initiation visit Follow up visit
Additional anti tumor treatment (name and dose)	exposure, potential confounder	Inclusion visit Follow up visit
Comedications (name of products, starting and ending dates)	exposure, potential confounder	Initiation visit Follow up visit
Sunitinib / Axitinib Progression (Y/N and date)	outcome	Initiation visit Follow up visit
Sunitinib / Axitinib Tumor Response	outcome	Initiation visit Follow up visit
Sunitinib / Axitinib Safety : AE description and AE grade (according CTCAE)	outcome	Initiation visit Follow up visit
Sunitinib / Axitinib discontinuation	outcome	Follow up visit
Axitinib QoL (FKSI-19, and MH and RE domains of SF-36)	outcome	Initiation visit Follow up visit End of treatment
Death (Y/N,date, Cause)	outcome	Follow up visit

Table 1 : variables collected during study

Detailed definitions will be included in the Statistical Analysis Plan

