8.7.3. Safety Analysis

Summaries and listings of AEs and other safety parameters will be provided by period of treatment (Sunitinib, Axitinib).

Frequencies of patients experiencing at least one AE will be displayed by body system and preferred term according to MedDRA terminology. Summary tables will present the number of patients observed with AEs and corresponding percentages.

The description will be conducted for all the reported AEs whether related to the drug or not, and then for the AEs related to SU or AXI.

Adverse event reported by patients through the quality of life questionnaires will also be described.

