10.3. DEFINITIONS OF SAFETY EVENTS

Adverse events

An AE is any untoward medical occurrence in a patient administered a medicinal product. The event need not necessarily have a causal relationship with the product treatment or usage. Examples of adverse events include but are not limited to:

 Abnormal test findings (see below for circumstances in which an abnormal test finding constitutes an adverse event/AR*);

^{*} Spain requirement only

- · Clinically significant symptoms and signs;
- Changes in physical examination findings;
- Hypersensitivity;
- Lack of efficacy;
- Drug abuse;
- Drug dependency.

Additionally, for medicinal products, they may include the signs or symptoms resulting from:

- Drug overdose;
- · Drug withdrawal;
- Drug misuse;
- Off-label use;
- Drug interactions;
- Extravasation;
- Exposure during pregnancy;
- Exposure during breast feeding;
- Medication error;
- Occupational exposure.

Abnormal test findings

The criteria for determining whether an abnormal objective test finding should be reported as an adverse event/AR* are as follows:

- Test result is associated with accompanying symptoms, and/or
- · Test result requires additional diagnostic testing or medical/surgical intervention, and/or

Pfizer Confidential Page 41 of 108

Spain requirement only

- Test result leads to a change in study dosing or discontinuation from the study, significant additional concomitant drug treatment, or other therapy, and/or
- Test result is considered to be an adverse event by the investigator or sponsor.

Merely repeating an abnormal test, in the absence of any of the above conditions, does not constitute an adverse event/AR*. Any abnormal test result that is determined to be an error does not require reporting as an adverse event/AR*.

Serious adverse events/SAR*

A serious adverse event/SAR* is any untoward medical occurrence in a patient administered a medicinal or nutritional product (including pediatric formulas) at any dose that:

- Results in death;
- Is life-threatening;
- Requires inpatient hospitalization or prolongation of hospitalization (see below for circumstances that do not constitute adverse events/AR*);
- Results in persistent or significant disability/incapacity (substantial disruption of the ability to conduct normal life functions);
- Results in congenital anomaly/birth defect.

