1.2. Study plan

Variable	At SU initiatio n visit	At SU follow-up visit	At AXI initiation visit	At AXI follow- up visit	Long term follow up
Patient demographics	x		x*		
Performance status	х	х	х	х	X
MSKCC risk, Heng risk	x		x		
Description of primary tumor	x		x*		
Metastasis	x		x		
Comorbidities	x		x		
Lab tests	x	x	x	х	
Blood Pressure measurement / antihypertensive treatment	х	х	х	x	
Electrocardiogram	x		х		
Echocardiography	x		x		
Sunitinib therapy	x	x	X**		
Axitinib therapy			x	x	
Other anti tumor treatment	x	x	x	x	X
Concomitant treatment	x	x	x	x	
Tumor Response		x		х	x
Safety	x	x	x	х	
Quality of life (FKSI-19, and MH and RE domains of SF-36)			х	х	
Death		х		X	x

^{*:} only if patient is enrolled at Axitinib start / **: retrospective records

ADONIS CRF

Subject ID:

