	□ст	☐ Chest X-ra	ay ☐ MRI	☐ Ultrasour	nd 🔲 Bone scan		
Resp	onse to therapy:						
	☐ CR (Complet	e Remission)					
	☐ PR (Partial R	•					
	☐ SD (Stable D	•					
	☐ PD (Progress						
Clinical par	□ NA (Not Asse	essable)	Reason:				
Chincai pa	ameters						
Blood pres	ssure measure	ement					
☐ Yes	□ No	If yes, please	specify date: /	/(DD/	MM/YYYY)		
Please specify	y levels; if several	measurements	have been done, pl	ease specify levels fo	r every measurement		
			Systolic (mmHg)	Diastolic (mmHg)			
	Measurement 1	☐ Not done					
	Measurement 2	☐ Not done					
	Measurement 3	☐ Not done					
Changes in the antihypertensive treatment since last visit:							
If yes, Date / / (DD/MM/YYYY							
If yes, changes in the antihypertensive treatment were							
	☐ dose increase ☐ dose reduction						
	□ char	nges of drugs					
		tional antihypert					
_	f drugs, please up stigator can update			ole (the table of concor	nitant treatment is displayed		
Eastern C	ooperative On	cology Gro	oup (ECOG) ava	ilable □ Yes	□ No		

ADONIS CRF								
If yes, □ 0	1 2 0	3 🗆 4						
Laboratory test rest	Laboratory test results							
New lab test results ☐ Ye	es □ No (the	CRF displays the d	ate of lab test	results at the last visi				
if yes date of the last lab t	test results/	/ (DD/MM/	YYYY)					
For the following parameters, please complete the table								
LABORATORY PARAMETERS	LEVEL OBTAINED	LEVEL*	UNIT	OTHER UNIT, IF APPLICABLE				
Hemoglobin	☐ Yes ☐ No		g/dL					
Calcium	☐ Yes ☐ No		mmol/L					
Albumin	☐ Yes ☐ No		g/L					
LDH	☐ Yes ☐ No		U/L					
Platelets	☐ Yes ☐ No		10 ⁹ /L					
Neutrophils	☐ Yes ☐ No		%					
LABORATORY PARAMETERS	ameters, please: indi LEVEL OBTAINED	LEVEL*	findings UNIT	OTHER UNIT, IF APPLICABLE				
Creatinine	☐ Yes		mg/dL					
ALT (GPT)	☐ Yes		U/L					
AST (GOT)	☐ Yes		U/L					
Alkaline phosphatase	☐ Yes		U/L					
Total bilirubin	☐ Yes		mg/dL					
TSH	☐ Yes		mU/L					
fT3	☐ Yes		pmol/L					
fT4	☐ Yes		pmol/L					
Hematocrit								
	□ Yes		%					
Phosphate	☐ Yes							
Phosphate Glucose			%					
Glucose Lymphocytes	☐ Yes ☐ Yes ☐ Yes		% mmol/L mmol/L %					
Glucose	☐ Yes ☐ Yes ☐ Yes ☐ Yes ☐ Yes		% mmol/L mmol/L					
Glucose Lymphocytes Leucocytes Sodium	☐ Yes		% mmol/L mmol/L % 10 ⁹ /L mmol/L					
Lymphocytes Leucocytes Sodium Potassium	☐ Yes		% mmol/L mmol/L % 10 ⁹ /L mmol/L mmol/L					
Glucose Lymphocytes Leucocytes Sodium	☐ Yes		% mmol/L mmol/L % 10 ⁹ /L mmol/L					

mmol/L

Triglycerides

□ Yes

Axitinib thei	rapy		Axitinib therapy					

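### On-treatment blood pressure is collected and labelled an outcome in the protocol, but no analysis in the SAP text uses it, so hypertension during treatment is reported only as an adverse event

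*SAP*

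**What the plan says.** **Protocol.** Table 1 (8.3) lists "Blood Pressure measurement (Y/N, date of exam and level, antihypertensive treatment") with the role "baseline characteristics, outcome", sourced from initiation and follow-up visits. Section 8.7.3 states: "Summaries and listings of AEs and other safety parameters will be provided by period of treatment (Sunitinib, Axitinib"). The background, under Gap 2, cites diastolic pressure of 90 mmHg or more as a correlate of axitinib efficacy in pooled phase II studies and remarks that "the association between hypertension, Axitinib titration and clinical outcome needs to be further investigated".

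**CRF (Annex 1).** The study plan (1.2) has a row "Blood Pressure measurement / antihypertensive treatment", ticked at sunitinib initiation, sunitinib follow-up, axitinib initiation and axitinib follow-up, but not at long-term follow-up. The sunitinib and axitinib follow-up forms take up to three systolic/diastolic pairs, if blood pressure was measured, and ask for "Changes in the antihypertensive treatment since last visit".

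**SAP.** Section 6.2 begins "The analysis of safety will be realized thanks to following endpoints" and gives three items: incidence of AEs, discontinuation due to toxicity, and deaths. Section 6.2.1 names hypertension among the AE types to be described however few patients have them. Section 8.2.1 analyses the same three items. Section 6.4 has medical history of hypertension as a possible covariate. Sections 8.2.5 and 8.2.6 describe patient characteristics at sunitinib and axitinib initiation.

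**The concern.** The protocol labels a variable an outcome, collects it at follow-up, and says that safety parameters other than AEs will be summarised. The SAP then gives a safety list with no place for it and does not say that it was dropped or why.

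What is at stake is the description of hypertension during treatment. Under the SAP as written it rests on what sites declare as AEs. Two features of the documents make that route incomplete. First, Protocol 10.3 sets conditions before an abnormal finding counts as an AE, so a rise that is recorded and only watched may never be declared. Second, the safety question on the axitinib follow-up form asks about events related to sunitinib, which puts AE capture during axitinib in some doubt. Recorded blood pressure depends on neither, so it would give an independent check on the AE rate.

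**Working it through.** The main check is a comparison of texts.

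**1. Where blood pressure is collected, and where the SAP uses it**

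| Data item | Collected | Used in the SAP text |
|---|---|---|
| Reading at initiation | Sunitinib and axitinib initiation forms | Yes, under the general descriptions in 8.2.5 and 8.2.6 |
| Reading at follow-up | Sunitinib and axitinib follow-up forms | No |
| Antihypertensive change on treatment | Same follow-up forms | No |
| Hypertension as an AE | AE tables and AE form | Yes, 6.2.1 and 8.2.1 |
| History of hypertension | Initiation forms and retrospective section | Yes, 6.4 (possible covariate) |

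Blood pressure is collected at 4 of the 5 visit types in the CRF study plan. The SAP text plans no analysis of follow-up values.

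**2. What the AE route captures.** Protocol 10.3 makes an abnormal finding reportable if any one of these applies: it comes with symptoms; it needs further testing or intervention; it leads to a change in study dosing, discontinuation, or significant added treatment; or "Test result is considered to be an adverse event by the investigator or sponsor". A raised reading that meets none of these is not an AE and reaches no table in SAP 8.2.1.

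**3. Who has readings in each period.** Protocol 8.5 plans 350 SU-AXI patients: about 225 enrolled at axitinib start and about 125 enrolled at sunitinib start.
- Axitinib period: all 350 can have readings.
- Sunitinib period: the retrospective section for the 225 asks only about hypertension history and antihypertensive use at sunitinib initiation. It holds no readings and no later antihypertensive changes. Within the SU-AXI group, sunitinib-period values can therefore exist for about 125 of 350 (125/350 = 36%).

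**4. Precision of a simple proportion.** The largest 95% half-width (normal approximation, proportion 0.5) is 1.96 × √(0.25/n).
- n = 350: 1.96 × √(0.25/350) = 1.96 × 0.0267 = 0.052. This is the same expression, and the same value, as the accuracy in Protocol Table 2.
- n = 250, assumed to show a reduced denominator: 1.96 × √(0.25/250) = 1.96 × 0.0316 = 0.062, also as in Table 2.

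The Clopper-Pearson interval that the SAP uses for proportions is slightly wider: about 5.4 points at 175/350 and about 6.4 points at 125/250.

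**5. Size of the under-count.** The documents do not give the share of raised readings that sites do not declare as AEs, so this cannot be calculated.

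**The case against.** The strongest reply is that blood pressure is neither an objective (Protocol 7.2) nor an endpoint (Protocol 8.1.1). The protocol's safety endpoint is a description of AEs, and the SAP delivers it. Protocol 8.7 lets the SAP modify the plan and asks for an amendment only for major changes to primary endpoints. The AE route is also reasonably strong. Hypertension is described whatever its frequency, and a reading that prompts intervention or significant added treatment already qualifies as an AE. What is left is mainly untreated, asymptomatic rises.

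Most of this stands, and it limits the weight of the point. It does not remove the mismatch: the protocol does call blood pressure an outcome and does promise safety parameters beyond AEs, and the SAP gives no reason for leaving them out. If new or increased antihypertensive treatment should already appear as AEs, tabulating the two together would show whether it does.

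A reader might infer more than the documents support:
- *That Gap 2 cannot be addressed.* It closes by saying that ADONIS will assess flexible dosing and the impact of titration; neither needs on-treatment blood pressure. The sentence on hypertension is background.
- *That hypertension is the harm the protocol ties most closely to axitinib.* The protocol does not rank harms. It discusses blood pressure as a possible marker of exposure and efficacy.
- *That readings exist at every visit for every patient.* They are recorded when taken in routine care, are absent from long-term follow-up, and do not exist for the retrospective sunitinib period.
- *That no table is planned anywhere.* SAP section 9 places the table shells in separate documents, not available here. The SAP text calls for no such table, which is as far as the claim can go.

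**Conclusion.** The point holds as a minor gap between protocol and SAP. On-treatment blood pressure and antihypertensive changes are collected, and blood pressure is labelled an outcome, but no analysis in the SAP text uses them. On-treatment hypertension is reported only as an AE, and raised readings outside the criteria in Protocol 10.3 need not appear in any safety table.

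The under-count has no size that the documents can supply. The information available is up to 350 patients in the axitinib period. The 5.2-point half-width assumes that all 350 contribute and uses the normal approximation. It is not a bound for a proportion restricted to patients below a cut-off at initiation with a later reading; at an assumed 250 patients the figure is 6.2 points. No primary endpoint and no titration analysis changes.

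**What to change.** Add descriptive tables to SAP 6.2 and 8.2.1, in the Safety Analysis Set: for the axitinib period in all SU-AXI patients, and for the sunitinib period only in patients enrolled at sunitinib start.

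- (a) Systolic and diastolic values at initiation and on treatment, with the maximum change.
- (b) The proportion with an on-treatment diastolic value of 90 mmHg or more, among those below 90 at initiation with at least one later reading, with a Clopper-Pearson interval. This is the cut that the background cites as an efficacy correlate; it serves here for tabulation only and implies no management rule.
- (c) The proportion starting or increasing antihypertensive treatment. The SAP should say how a first start is identified, because the follow-up form lists dose increase, dose reduction, change of drug and additional therapy, with no separate entry for a first start.

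Show (b) and (c) beside the hypertension AE rate, and give the number of patients measured in each table. If the sponsor prefers not to analyse these data, the SAP should say so and reconcile this with the outcome label in Protocol Table 1. If blood pressure is ever related to PFS, only readings up to a fixed landmark should be used.

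The cost is SAP wording and two or three tables from data already in the eCRF. The drawback is that readings come from routine visits at irregular times, so patients seen more often have more chances to record a high value; the counts of patients measured help to show this.

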6.2.1 Incidence of Adverse Events (AEs)

- Incidence of AEs: Proportion of patients experiencing at least one AE of any grades by Body system (System Organ Class (SOC) MedDRA);
- Incidence of most common AEs of any grade (occurring in more than 10% of patients in either group) by preferred term (PT) (MedDRA);

The following type of AEs will be described whatever the number and proportion of patients concerned: Diarrhea, hypertension, fatigue, asthenia, hand foot syndrome, nausea, stomatitis, neutropenia, lymphopenia and increased lipase

- Incidence of serious AEs;

- Incidence of non-serious AEs;
- Incidence of all AE per grade, especially grade 3 and 4 AE. Note: all grades should be considered for this analysis and not only worst grade.

AEs will be analysed separately for AEs related to SU or AEs related to AXI treatment

6.2.2 Discontinuation due to Toxicity

- Proportion of patients who discontinued the treatment of interest, because of AEs;

Note: All discontinuations due to AE should be considered: those reported on SU/AXI follow-up forms and those reported on AEs form

- Treatment duration until discontinuation for AEs;

6.2.3 Deaths

- Proportion of patients who died due to any cause;
- Cause of death (tumor-related, other cause). In case of multiple cause of death, the cause from the Study Discontinuation form will be take into account in first.

6.3 OTHER ENDPOINTS

6.3.1 Axitinib Treatment

The real-life usage of AXI treatment will be analyzed with following endpoints:

AXI dose at initiation

- Proportion of patients with the recommended starting dose of AXI (5 mg BID)
- Proportion of patients with other starting doses

Dosing schedules over AXI treatment period

- Average/median total daily dose (mg) received over the AXI treatment period (i.e. at each study visit);
- Dose intensity of AXI: defined as the sum of AXI daily doses divided by the duration of AXI treatment in days (delay between the first AXI dose and the last dose, including temporary interruption).

Note: Axitinib discontinuation date will the Date of progression/intolerability or death reported at time of Axitinib discontinuation (cf. CRF page 35)

- Proportion of patients with at least one modification of the dose during treatment.
- Proportion of patients with at least one modification of the dose or at least one temporary interruption during treatment.
- Proportion of patients with at least one temporary interruption during treatment.
- Among patients with at least one temporary interruption, sum of all durations of temporary interruption by patient.
- Proportion of patients for whom the dose was reduced
- Proportion of patients for whom the dose was increased

AXI interruption and discontinuation

- Proportion of patients with temporary interruption during the AXI treatment period and reasons (AEs, radiotherapy, surgery, other);

- (Median) duration of the first interruption (days) and of all interruptions together;
- Proportion of patients with AXI discontinuation and reasons (progression, intolerability, death or other reason).

6.3.2 Sunitinib Treatment

- Proportion of patients with the recommended starting dose of Sunitinib
- Proportion of patients with other starting doses
- Proportion of patients with at least one modification of the dose
- Proportion of patients with at least one modification of the dose or at least one temporary interruption during treatment.
- Proportion of patients with at least one temporary interruption during treatment.
- Among patients with at least one temporary interruption, sum of all durations of temporary interruption by patient

